5.9.2 Disposition of Study Subjects

Subject disposition will be summarized in total and by procedure group and procedure subgroups using counts and percentages. The number and percentage of subjects completed and discontinued will be tabulated along with the specific reasons for discontinuation.

5.9.3 Demographic, Baseline, and Surgical Characteristics

Summary statistics of subject demographics (age, gender, and race) will be presented in total and by procedure group and procedure subgroups. Surgical characteristics including, at minimum, estimated blood loss, requirement for blood transfusion, and procedure duration will be summarized by procedure group, procedure subgroup and in total.

5.9.4 Primary and Secondary Endpoint Analyses

The number and percentage of vessels where hemostasis is achieved (≤ Grade 3) will be summarized and an exact 95% confidence interval will be estimated for each procedure group, procedure subgroup, and in total based on Clopper-Pearson's method. The performance goal hypothesis will be tested as described in Section 5.4.

The analysis of primary endpoint is based on the assumption of independence of hemostatic grades within subject and procedure. This assumption of independence and its impact on the overall study conclusion will be evaluated through sensitivity analyses and will be described in SAP.

Counts and percentages will be provided for type, size, and number of vessels transected, as well as for the grading scale distribution for all vessels transected, number of times ENSEAL X1 touch-ups were required, incidence of requirement for additional measures to obtain hemostasis on vessels (other advanced energy devices or hemostatic measures), and 5-point scale scores for various tasks completed by the ENSEAL X1 device (adhesiolysis, lymphatics or tissue bundles divided, tissue grasping, tissue cutting, or tissue dissection).

All device-related and procedure-related AEs reported during the study will be coded to MedDRA. All AEs will be summarized by MedDRA system organ class and preferred term by procedure group, procedure subgroup, and in total. Separate summaries will be provided for device-related and procedure-related AEs. Serious AEs will be summarized in a similar manner.

5.9.5 Plans for Interim Analyses

No interim analyses are planned for this study.

Study Number: ENG_2019_01 Version: Amendment 5

5.9.6 Handling of Missing Data

All summaries will be performed only on subjects undergoing the scheduled procedure and only observed data will be summarized. There will be no imputation of data for early terminated subjects or for missing data within the database.

5.9.7 Subgroup Analyses

Subgroup analyses are planned to be performed for the subgroup of subjects who have a medical history of treatment for cancer (e.g. chemotherapy or radiation) and may be performed for additional groups pending the distributions of baseline demographic or clinical characteristics. These analyses will be exploratory and summary statistics for the procedure-related parameters will be provided for each subgroup.

6.0 ADVERSE EVENTS

Only AEs considered possibly, probably, or causally related to the device or the procedure will be collected during this study.

6.1 DEFINITIONS

6.1.1 Adverse Event

An AE is defined as any untoward medical occurrence, regardless of its relationship to the study device or the study procedure. An untoward medical occurrence includes any new, undesirable medical experience or worsening of a pre-existing condition, which occurs throughout the duration of the clinical study.

6.1.2 Serious Adverse Event

It is the Investigator's responsibility to determine the "seriousness" of a reportable AE.

A SAE is defined as an AE (as defined in Section 6.1.1) that results in any of the following:

- Death;
- A life-threatening illness or injury;
- A permanent impairment of a body structure or a body function;
- Required in-patient hospitalization or prolongation of existing hospitalization;
- Resulted in medical or surgical intervention to prevent life-threatening illness or injury or permanent impairment to a body structure or a body function;
- Led to a fetal distress, fetal death, or a congenital abnormality or birth defect.

Note: "Death" should not be reported as an AE. The cause of death should be reported as the AE. The only exception is "Sudden Death" when the cause is unknown.

Note: Planned hospitalization for a pre-existing condition, or a procedure required by the protocol, without serious deterioration in health, is not considered a SAE.

6.1.3 Pre-existing Condition

A pre-existing condition is defined as a medical condition that is present at the initiation of the study and is to be reported as part of the subject's medical history with a listed start date. Any pre-existing condition that has worsened in intensity, frequency, or the character of the condition should be recorded as a new AE on the AE eCRF, as an exacerbation of the pre-existing condition and the start date will be recorded as the time when the exacerbation occurred.

6.2 SEVERITY OF ADVERSE EVENTS

It is the Investigator's responsibility to assess the severity of an AE. A change in severity may constitute a new reportable AE.

The following guideline should be used to determine the severity of each AE:

- **MILD:** A type of AE that is usually transient and may require only minimal treatment or therapeutic intervention. The event does not generally interfere with usual activities of daily living.
- MODERATE: A type of AE that is usually alleviated with additional specific therapeutic intervention. The event interferes with usual activities of daily living, causing discomfort but poses no significant or permanent risk of harm to the research participant.
- **SEVERE**: A type of AE that interrupts usual activities of daily living, or significantly affects clinical status, or may require intensive therapeutic intervention.

6.3 RELATIONSHIP OF ADVERSE EVENTS

It is the Investigator's responsibility to assess the relationship of a reportable AE (as defined in Section 6.1.1). Only AEs considered possibly, probably, or causally related to the study procedures or the ENSEAL X1 or GEN11 devices are to be recorded in the eCRF and reported to the Sponsor.

The following guidelines should be used in determining the relationship of an AE in the study:

- Not related Relationship to the procedures or device can be excluded when:
 - The event is not a known side effect of the product category the device belongs to or of similar devices and procedures;
 - The event has no temporal relationship with the use of the device or the procedures:
 - The event does not follow a known response pattern to the device (if the response pattern is previously known) and is biologically implausible;
 - The discontinuation of the device application or the reduction of the level activation/exposure (when clinically feasible) and reintroduction of its use (or increase of the level of activation/exposure), does not impact on the event;
 - The event involves a body-site or an organ not expected to be affected by the device or the procedure;
 - The event can be attributed to another cause (e.g. an underlying or concurrent illness/clinical condition, an effect of another device, drug, treatment, or other risk factors);
 - Harms to the subject are not clearly due to use error; or
 - To establish the non-relatedness, not all the criteria listed above might be met at the same time, depending on the type of device/procedure and the event.
- **Possible** The relationship with the use of the device is weak but cannot be ruled out completely. Alternative causes are also possible (e.g. an underlying or concurrent illness/condition and/or an effect of another device, drug, or treatment).

Version: Amendment 5

Cases where relatedness cannot be assessed or no information has been obtained should also be classified as possible.

- Probable The relationship with the use of the device seems relevant and/or the
 event cannot reasonably be explained by another cause, but additional information
 may be obtained.
- **Causal relationship** The event is associated with the device or with procedures beyond reasonable doubt when:
 - The event is a known side effect of the product category the device belongs to or of similar devices and procedures;
 - The event has a temporal relationship with the device uses/application or procedures;
 - The event involves a body-site or organ that:
 - The device or procedures are applied to;
 - The device or procedures have an effect on;
 - The event follows a known response pattern to the medical device (if the response pattern is previously known);
 - The discontinuation of medical device application (or reduction of the level of activation/exposure) and reintroduction of its use (or increase of the level of activation/exposure), impact on the event (when clinically feasible);
 - Other possible causes (e.g. an underlying or concurrent illness/clinical condition and/or an effect of another device, drug, or treatment) have been adequately ruled out;
 - Harm to the subject is due to error in use; or
 - To establish the relatedness, not all the criteria listed above might be met at the same time, depending on the type of device/procedure and the event.

6.4 REPORTING PROCEDURES FOR ADVERSE EVENTS

6.4.1 Recording Adverse Events

The Investigator will record all AEs (both AEs and SAEs) considered attributable (relationship of possible, probable, causal relationship) to the study procedure or the ENSEAL X1 or GEN11 devices in the source documents and eCRF.

Standard medical terminology should be used when recording AEs. In addition, the following information should be recorded:

- Onset date:
- Resolution date or date of death;
- Severity of the event;
- Indication of whether the event is serious;
- Relationship of AE to the study devices;
- Relationship of AE to the study procedure;
- Action taken;
- Event status; and
- Was AE anticipated or not (only for SAEs).

Data related to AEs will be collected until the event resolution, or until the event is

considered stable, or until all attempts to determine the resolution of the event are exhausted. All AEs that are unresolved at study completion (or at the last visit completed for early withdrawal subjects) will be recorded as ongoing at study end.

6.4.2 Reporting Adverse Events

The Investigator is required to report AEs to the Sponsor within 2 weeks from when the study site becomes aware of the event. All AEs must be reported on the AE eCRF and be documented in a timely manner throughout the study duration.

6.4.3 Reporting Serious Adverse Events

Any AE that the Investigator determines to be a SAE must be reported by the study site within 72 hours of becoming aware of the event to the Sponsor by completing the AE eCRF. A notification containing the pertinent data will be automatically generated by the EDC system and forwarded to the Sponsor. If applicable, supporting SAE documentation should be de-identified and provided to the Clinical Trial Leader. The report of an SAE by a study site does not constitute an admission that study personnel or the user facility (hospital/clinic) caused or contributed to the event. The study site is also responsible for submitting SAEs to the reviewing IRB/EC per their IRB/EC procedures.

7.0 PRODUCT COMPLAINTS

A product complaint is any written, electronic, or oral communication that alleges deficiencies related to the identity, labeling, quality, durability, reliability, safety, effectiveness, or performance of a device after it is released for distribution. A product complaint may or may not be associated with an AE/SAE.

7.1 REPORTING PRODUCT COMPLAINTS FOR MARKETED DEVICES

7.1.1 Reporting of Approved EES Marketed Devices

All product complaints related to devices in the procedure shall be documented throughout the clinical investigation. Product complaints related to an Ethicon-manufactured ENSEAL X1 or GEN11 devices must be reported to the Sponsor in a timely manner and no later than 24 hours after becoming aware of the event. When a sponsor representative becomes aware of a product complaint, the Product Complaint Team must be notified within 24 hours after becoming aware of the event. The Product Complaint Form must be emailed to the Sponsor Customer Complaint team at the following email address:

[contact]

The sites will report Product Complaints by completing the Product Complaint Form. If a product complaint is related to a safety event, the site must complete an AE eCRF as well. One copy of the processed form should be kept on-site and the device should be retained. Sponsor representatives will organize collection of the device for evaluation as needed.

7.1.2 Reporting of Approved Marketed Devices and Commercially Available Devices (not Ethicon)

The site should report Product Complaints of non-Ethicon devices that are approved marketed devices or commercially available medical devices according to the specific product's manufacturer specifications/guidelines.

Study Number: ENG_2019_01 CONFIDENTIAL Page 33 of 34 Version: Amendment 5 11 NOV 2022

1.1 Study Objectives

The primary objective of this study is to demonstrate the acceptable performance and safety of the ENSEAL X1 and GEN11 devices when used per the instructions for use (IFU).

1.2 Study Design

This prospective, single-arm, multi-center study will collect clinical data in a post-market setting by procedure group (upper gastrointestinal (GI), lower GI, and gynecological). Investigators will perform each procedure using the device in compliance with their standard surgical approach and the ENSEAL X1 and GEN11 IFUs.

Subjects will be consented and screened anytime during a period of 8 weeks prior to the date of surgery. Subjects will be considered enrolled when the ENSEAL X1 device has been attempted to be used for a vessel transection during upper GI, lower GI, or gynecological procedures. All enrolled subjects will be followed post-operatively through discharge and again at 28 days (\pm 14 days) post-surgery; therefore, from the surgery date to study exit, the duration will be approximately 6 weeks.

A minimum of 133 subjects (maximum of 149 subjects) will be included in the study from up to 16 surgery centers in the United States and/or European Union and/or United Kingdom. The enrollment is planned with the following procedure targets:

- A minimum of 77 subjects enrolled to a maximum of 89 subjects enrolled for upper GI procedures to achieve 27 vessel transections in each of the four procedure subgroups.
 Subjects will be enrolled to the following procedure subgroups with corresponding enrollment restrictions:
 - A minimum of 14 subjects enrolled to a maximum of 17 subjects enrolled for fundoplication (Nissen, anterior or posterior [Toupet]) or hiatal hernia procedures);
 - A minimum of 27 subjects enrolled to a maximum of 30 subjects enrolled for gall bladder procedures;
 - A minimum of 10 subjects enrolled to a maximum of 13 subjects enrolled for sleeve gastrectomy procedures;
 - A minimum of 26 subjects enrolled to a maximum of 29 subjects enrolled for small intestine resection procedures (also includes Roux-en-Y gastric bypass [RYGB] and biliopancreatic diversion with duodenal switch [BPD/DS]);
- A minimum of 28 subjects enrolled to a maximum of 30 subjects enrolled for lower GI procedures (e.g., large intestine resections); and
- A minimum of 28 subjects enrolled to a maximum of 30 subjects enrolled for gynecological procedures (hysterectomies associated with oophorectomies).

2 Treatment Assignment

This is a single-arm study where all enrolled subjects will have the ENSEAL X1 device utilized for transection of at least one vessel.

3 Randomization and Blinding Procedures

As this is a single-arm study, no randomization will occur, and no blinding procedures are required.

4 Interval Windows

Interval windows for the purpose of analysis in this study will not be defined outside of those already specified in the protocol for visit scheduling as the collection of data for the primary and secondary performance endpoints occurs intra-operatively. The final visit occurs approximately 4 weeks after surgery, thus no interval windows need to be defined given the absence of long-term follow-up in this study. The Schedule of Events specifies a window of 14 days around the scheduling of the 4-week follow-up visit, and any information entered in the eCRFs at this visit will correspond to the 4-week visit. There will be no assigning of observations to time points outside of the visit to which they are recorded in the eCRFs.

5 Levels of Significance

The statistical hypothesis for the primary endpoint will be evaluated using a one-sided significance level of 0.025. A 95% confidence interval will be provided for the primary endpoint. Estimation of primary endpoint by procedure group and procedure subgroup will provide 95% confidence interval. Estimation of secondary and safety endpoints will be summarized by number and percentages only.

6 Analysis Sets

Full Analysis Set: Full Analysis Set (FAS) will include subjects for whom the ENSEAL X1 device is utilized during the surgical procedure and have assessment for the primary endpoint. The FAS includes subjects for whom the answer is "Yes" to at least one of the following questions from the "ENSEAL X1 Usage" form on eCRF: "Were adhesions removed or divided by ENSEAL X1", "Were lymphatics bundles divided by ENSEAL X1", "Were tissue bundles divided by ENSEAL X1", "Was the ENSEAL X1 used for tissue grasping", "Was the ENSEAL X1 used for tissue dissection." The summary of all primary and secondary performance endpoints will be performed using FAS by procedure group (upper GI, lower GI, and gynecological), procedure subgroup (fundoplication, gall bladder, sleeve gastrectomy, and small intestine resection) and on the entire pooled set of subjects.

Safety Analysis Set: The Safety Analysis Set (SAS) will include all subjects who signed informed consent and for whom the ENSEAL X1 device is utilized during the surgical procedure. The safety endpoints will be summarized using SAS by procedure group, procedure subgroup and in total.

All Enrolled Set: The All Enrolled Set (AES) contains all subjects who provide informed consent for this study. The AES will be used for disposition of study subjects and for all listings.

7 Sample Size Justification

A sample size of at least 230 vessel transections is required to have a minimum of 90% power for rejecting the null hypothesis when the expected rate of Grade 3 hemostatic transections is at least 94.0% based on exact binomial test and a one-sided significance level of 0.025. The hemostatic transection grades for vessels are assumed to be independent within a subject and within a procedure.

In order to achieve a total of 230 vessel transections for analysis with a minimum of 27 vessel transections in each group (including 4 procedure subgroups in upper GI procedure), a minimum of 122 subjects (a maximum of 149 subjects) will be enrolled in the study.

The original sample size of the study was based on the assumption of one vessel transection per subject. At the time of amendment 5 the number of transections per subject was estimated to be 1.9 on average. The primary endpoint and the study hypothesis are based on hemostasis of vessel transection; therefore, the number of subject to be enrolled was updated to ensure 230 vessel transections.

Given that the primary endpoint is being evaluated intra-operatively, it is not anticipated that there will be subject dropout prior to evaluating this endpoint, thus no adjustment or increase in subject enrollment is planned to account for dropout. A minimum of 27 vessel transections in each group (including 4 procedure subgroups in upper GI procedure) is planned to attain optimum representation of each of the procedure groups to the whole study sample.

From a safety perspective on the pooled analysis of 133 subjects and in consideration of rare AEs that may occur (e.g., bleeding requiring blood product transfusion), for an event that has an incidence rate of, for example, 1%, then in a sample of 133 subjects, the probability of observing at least 1 event is 73.7% under a binomial probability model. Thus, this sample size provides a high probability of observing rare events if they do occur, and provides reasonable assurance to conclude that the likelihood of such AEs is less than 2.8% if they do not occur based on the upper limit of an exact 95% confidence interval when 0 events out of 133 subjects are observed.

8 Analyses to be Conducted

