2.3 SAFETY ENDPOINT

The safety endpoint will be occurrence of device-related adverse events (AEs).

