5.5 LEVELS OF SIGNIFICANCE

The hypotheses above will be evaluated using a one-sided significance level of 0.025. Estimation of all additional endpoints will be performed using 95% confidence intervals.

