5.9 ANALYSES TO BE CONDUCTED

5.9.1 General Conventions

Categorical variables will be summarized descriptively by frequencies and associated percentages. Continuous variables will be summarized descriptively by number of subjects, mean, standard deviation, median, minimum, and maximum. Confidence intervals will also be provided for procedure-related variables

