8.5 Safety Analyses

The primary safety endpoint in this study is the occurrence of device-related adverse events (AEs). As per the study protocol, device-related AEs are those identified as having a relationship of possibly, probably, or causally with the ENSEAL X1 or GEN11 devices. AEs unrelated to the study device are recorded as 'not related' on the CRF. Both device-related and procedure-related AEs reported during the study will be coded to MedDRA. All reported AEs will be summarized by MedDRA system organ class and preferred term by procedure group, procedure subgroup, and in total. Separate summarizes will be provided for device-related and procedure-related AEs. Serious AEs will be summarized in a similar manner. All safety endpoints will be summarized by procedure group, procedure subgroup, and in total. All reported adverse events will be listed. Listings will also be provided for blood transfusion details, concomitant procedures, and concomitant medications.

Safety endpoints are as follows:

- All AEs
- Serious AEs
- All AEs related to the study device
- Serious AEs related to the study device
- All AEs related to the study procedure
- Serious AEs related to the study procedure

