8.5.1 Safety Outcomes Reported in the CER

Safety outcomes identified in the CER # SCN060262 (ref. Table 33) will be summarized by procedure group, procedure subgroup, and in total. Only key safety outcomes that include major bleeding as defined as hemorrhage > 400 mL and thermal damage/injury will be presented. The observed event rates for the key safety outcomes from current study will be presented along with the median event rates from the CER for descriptive comparison. No statistical test will be conducted.

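### SAP 5 drops the 95% intervals that Protocol 5.5 plans for secondary and safety endpoints, and SAP 7 states a minimum of 122 subjects where the consistent figure is 133

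*SAP*

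**What the plan says.** **Intervals.** Protocol 5.5, after setting the level for the primary hypothesis, states: "Estimation of all additional endpoints will be performed using 95% confidence intervals". Protocol 5.9.1 adds: "Confidence intervals will also be provided for procedure-related variables". The SAP section with the same title, SAP 5, keeps the interval for the primary endpoint (overall, by procedure group and by subgroup) and then says: "Estimation of secondary and safety endpoints will be summarized by number and percentages only". SAP 8.1 lists the summary statistics to be used and includes no interval.

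**Safety.** Protocol 2.3 names one safety endpoint: "The safety endpoint will be occurrence of device-related adverse events (AEs"). SAP 1.1 gives the primary objective as "to demonstrate the acceptable performance and safety of the ENSEAL X1 and GEN11 devices". For the analysis, SAP 8.5 says "All reported AEs will be summarized by MedDRA system organ class and preferred term", by procedure group, subgroup and in total, with no interval. SAP 8.5.1 takes two key outcomes (major bleeding and thermal injury) whose observed rates "will be presented along with the median event rates from the CER for descriptive comparison", again with no interval and no test.

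**Subjects.** SAP 7 gives a minimum of 122 subjects and a maximum of 149. SAP 1.2 and Protocol 5.7 give 133 and 149, as do the Protocol synopsis and Protocol 3.2.1. The safety paragraph in SAP 7 is itself worked for 133.

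**The concern.** The two sections on significance levels give opposite instructions. The SAP sentence ends in an explicit exclusion, so it cannot be read as silence that the Protocol fills. The SAP does not record it as a departure: SAP 8.1 asks for documentation only when a final analysis differs from the SAP, not when the SAP differs from the Protocol.

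Safety has no hypothesis and no threshold, so the device-related event rate will be judged descriptively. Its precision is then the main guide to what the rate supports. A reported 0% carries very different information in a column of 28 subjects and in one of 133. SAP 7 also justifies the sample size for safety by an exact 95% upper limit, which SAP 5 then leaves out of the safety analysis.

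The figure of 122 is a separate matter. It is a stated sample size that disagrees with the rest of both documents and with the calculations two paragraphs below it.

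**Working it through.** **1. The plan's own safety figures (SAP 7, Protocol 5.7)**

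Inputs: 133 subjects, event rate 1%, zero events for the upper limit.

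- Chance of at least one event: 1 − 0.99^N. For N = 133 this is 73.7%, as stated.
- Exact two-sided 95% upper limit for 0 of N: 1 − 0.025^(1/N). For N = 133 this is 2.74%, which agrees with the stated bound of less than 2.8%.
- For N = 122 the same formulas give 70.7% and 2.98%. The 2.8% bound would then be false.

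**2. What the missing intervals would show**

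Method: Clopper-Pearson, counting each subject once (at least one device-related event or none). For x events in N subjects, the lower limit is the 0.025 quantile of Beta(x, N − x + 1), or 0 when x = 0. The upper limit is the 0.975 quantile of Beta(x + 1, N − x). N is the enrollment minimum in SAP 1.2: 133 overall, 77 for upper GI, 28 each for lower GI and gynecological. The event counts are illustrative, because the documents give no expected rate.

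| Events / subjects | Observed | Exact 95% interval |
|---|---|---|
| 0 / 133 | 0% | 0 to 2.74% |
| 1 / 133 | 0.75% | 0.02 to 4.12% |
| 3 / 133 | 2.26% | 0.47 to 6.45% |
| 0 / 77 | 0% | 0 to 4.68% |
| 1 / 77 | 1.30% | 0.03 to 7.03% |
| 0 / 28 | 0% | 0 to 12.34% |
| 1 / 28 | 3.57% | 0.09 to 18.35% |

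**3. 122 against 133**

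- Upper GI minimums: 14 + 27 + 10 + 26 = 77. With lower GI and gynecological: 77 + 28 + 28 = 133.
- Maximums: 17 + 30 + 13 + 29 = 89, and 89 + 30 + 30 = 149. So the 149 in SAP 7 does follow the group targets.
- Likely source of 122: 230 transections at 1.9 per subject is 230 / 1.9 = 121.05, rounded up to 122. That covers the total only. The SAP 7 sentence also claims to cover the requirement of 27 transections per group, for which the enrollment minimums sum to 133. The shortfall is 133 − 122 = 11 subjects.
- Expected transections: 122 × 1.9 = 231.8 and 133 × 1.9 = 252.7. Both exceed 230 on average.

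**4. Is the primary test touched?**

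Exact binomial, 230 transections, goal 87.5%, expected rate 94.0%, one-sided 0.025. The smallest number of successes whose upper-tail probability under 87.5% is at most 0.025 is 212 (tail 0.0161). The power at 94.0% is 0.9002, so the stated 90% at 230 reproduces. Neither point changes it.

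**The case against.** The best defence is that the Protocol is not consistent with itself. Protocol 5.9.4 names an exact interval for the primary endpoint, then plans only counts and percentages for the grading distribution and the 5-point scores. For adverse events it plans MedDRA tables and says "Separate summaries will be provided for device-related and procedure-related AEs", again with no interval. The SAP follows that more specific text, and Protocol 5.0 describes its statistics as an overview to be detailed in the SAP. On this reading the stray sentence is the general one in Protocol 5.5. This part stands: the conflict is with a general rule, and for consistency alone a stated reason would settle it. But 5.9.4 is silent on these intervals where 5.5 is explicit, and the SAP gives no reason.

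Other points also stand in part:

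- The tables will show denominators, so a reader can work out the interval. The effect is on reporting and on agreement between documents.
- Protocol 5.5 does not ask for intervals by procedure group, and it does not reach the two outcomes in SAP 8.5.1, which are not Protocol endpoints.
- Protocol 5.9.1 does not define procedure-related variables, so no specific omission can be shown there. The SAP can only be asked to say what was decided.
- The group minimums in SAP 1.2 already hold enrollment at 133, so 122 is unlikely to be acted on. It is still a wrong figure in the sample size section.

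**Conclusion.** Both parts hold. SAP 5 departs from Protocol 5.5 without explanation, and on the SAP text the only safety endpoint in the Protocol would carry no measure of precision. With zero events, the unreported exact upper limit is 2.74% at 133 subjects, 4.68% at 77 and 12.34% at 28. With one event, the limits are 4.12%, 7.03% and 18.35%. The minimum of 122 in SAP 7 is 11 subjects below the sum of the group minimums and contradicts the safety figures in the same section.

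The consequence is moderate: no hypothesis, success criterion, power figure or data collection changes. The conclusion rests on the SAP text, since the table shells (SAP Appendix) were not available and could contain intervals. The limits assume that each group in the Safety Analysis Set is exactly at its enrollment minimum.

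**What to change.** - **SAP 5 and 8.5:** report the exact (Clopper-Pearson) 95% interval for the proportion of subjects with at least one device-related adverse event, overall and by procedure group. The overall interval follows Protocol 5.5 and is the quantity SAP 7 relies on. The by-group intervals are a recommendation.
- **SAP 8.5.1:** preferably give the same interval for the two observed rates shown beside the CER medians. The Protocol does not require this.
- **Secondary endpoints:** if they stay at counts and percentages, say so in SAP 5 as a departure from Protocol 5.5, with the reason. That is reasonable for distributions over several categories and agrees with Protocol 5.9.4.
- **Protocol 5.9.1:** state in SAP 8.1 whether the intervals for procedure-related variables are kept and, if so, for which variables.
- **SAP 7:** correct the minimum from 122 to 133.

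The cost is a few sentences, one corrected number and one interval added to the device-related event summary, with no new data. The drawback is that intervals in the small groups will be wide (upper limit 12.3% with 0 of 28), which reflects what those groups can show.
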